## **D.1 Data Management and Analysis**

**D.1.a. Assessment Measures:** The primary outcome measure is the number of patients who complete an SLT over the study period. Rates of SLT procedures will be compared between patients enrolled in the SLT Educational Intervention group versus the Usual Care group. Rates of SLT will be tracked in each group after patients are asked the first set of questions and after the Intervention group is shown the video. Follow-up eye exam appointments for patients in both groups will be tracked for a 6-month period to assess the number of patients who elect to have SLT.

The secondary outcome is to assess the beliefs and attitudes of patients and a group of ophthalmologists about SLT as first line therapy before and after viewing Educational Intervention. The research coordinator will ask all patients questions about their knowledge, beliefs, barriers, and attitudes about SLT vs. medication as first line treatment of glaucoma. These questions will be developed with [name], a psychologist and vision researcher at Sidney Kimmel Medical College with extensive experience in survey development and sampling techniques. She will be consulted during the development phase to revise and implement the following questions. If a more understandable explanation of the risks/benefits of SLT versus medications results in a significant increase in SLT treatments, that suggests that the real barrier is patient understanding and perhaps to a lesser extent physician education.

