### **C.3. Recruitment and Inclusion Criteria:**

**Patients:** A total of 40 patients will be recruited from the Wills Eye Hospital Glaucoma Care Specialists' private practice and the resident-run Glaucoma Clinic over an 6-month period for this pilot study. Eligible patients will be between 40 and 90 years of age, and have either high-risk ocular hypertension, primary open-angle glaucoma, or pseudo-exfoliation glaucoma with no previous laser trabeculoplasty. Eligible patients will be naive to medication and laser **or** currently being treated with glaucoma eye drop(s). Only patients within three years of a glaucoma-related diagnosis and stable intraocular pressure will be invited to participate.

After IRB approval, the patients' electronic medical records will be reviewed in advance of their next scheduled eye exam. Eligible patients will be invited to participate in the study by letter and/or telephone call, in advance of their scheduled appointment. Eligible patients may also be approached by our study team when checking in on the same day of their eye exam appointment.

All patients will be asked to provide written informed consent, prior to meeting with their ophthalmologist. Once patients are consented, a yellow-colored page with large font (**Patient Enrolled: SLT vs. Meds Study**) will be inserted into the patient's medical chart folder to alert the doctor that the patient is enrolled in the study and that both treatment options should be discussed in detail.

Those enrolled will be randomized to either the SLT Educational Intervention group (n=20) or the Usual Care group (n=20). The knowledge, beliefs, barriers, and attitudes about SLT vs. medication as first line treatment of glaucoma will be assessed in both groups.

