#### **C.4. Study Procedures:**

**Educational Intervention group:** The 20 patients randomized to the SLT Educational Intervention group will meet with their ophthalmologist who will discuss both SLT and medication options for treatment of glaucoma, which is currently standard of care. After their eye exam, the patient will meet with the research coordinator. The research coordinator will then ask the patient questions to assess their knowledge, beliefs, barriers, and attitudes about SLT vs. medication as first line treatment of glaucoma (See section D.2.a). The patient will then review the SLT Educational Intervention and be shown the PowerPoint presentation about SLT. After the presentation, the patient will be asked more questions (See section D.2 b). After viewing all information, the Intervention patient will have the opportunity to ask questions to the research coordinator about SLT. If the patient elects to schedule an SLT after the Educational Intervention, they will be assisted with making this appointment.

**Usual Care group procedures:** The 20 patients randomized to the Usual Care group will meet with their ophthalmologist who will recommend both SLT and medication options for treatment of glaucoma, which is currently standard of care. After their eye exam, the patient will meet with the research coordinator who will answer any questions they have about treatment options. The research coordinator will then ask the patient questions to assess their knowledge, beliefs, barriers, and attitudes about SLT vs. medication as first line treatment of glaucoma (See section D.2.a). The Usual Care group will not be exposed to SLT Educational Intervention and will not be asked to watch a video about SLT. If the patient elects to have SLT at any point during the study, we will provide the phone number for them to schedule the procedure. Patients in the Usual Care group will not be assisted with making any SLT appointments.

If patients in either group would like to consult with their ophthalmologist again, we will provide a message to the physician and he/she will call the patient to discuss treatment options again. Doctors will be masked to the group assignment to reduce biasing the outcome. We will track how many patients wanted to speak to their ophthalmologist over the phone or in person in both groups and the outcome of these calls.

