**D.2.a. Questions for Patients in Both Groups after Consenting and Eye Exam**

Are you aware that glaucoma can be treated with laser therapy instead of eye drops?  
Did you know that laser therapy is a possible first option for treating glaucoma before eye drops?  
Did you discuss laser therapy with your glaucoma doctor today?  
Would you consider having laser treatment? Why or why not?  
Would you consider having this laser therapy instead of filling your prescription for eye drops?  
If no, please describe reasons.

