**D.2.d. Ophthalmologists' Questions After Viewing the Presentation and Video:**

- 1) Did this educational program convince you that SLT is appropriate as first line therapy instead of medication? Why or why not?
- 2) If you are reluctant to recommend SLT as first line therapy, please explain why.
- 3) What additional information would you like to know to help make an informed decision?

**E. Study Timeline:** The study will be conducted between July 1, 2017 and June 31, 2018. We will complete all IRB submission and staff training prior to July 1, 2017. We will develop the Educational Intervention and video during the initial 3 months of funding period. We will identify, recruit, consent and enroll 40 patients, who will be randomized, 20 to the Educational Intervention group and 20 to the Usual Care group between August 1, 2017 and January 30, 2018. Data cleaning, analysis, and dissemination of findings will be completed by June 30, 2018 and a dissemination plan will be implemented to include submitting publication and

abstracts for presentations at national research meetings such as American Glaucoma Society and American Academy of Ophthalmology.

**F. Statistical Analysis:** All data analyses will be conducted using R (R core team, Vienna, Austria). Fisher's exact test for count data will be used to compare the pre- and post-SLT Educational Intervention survey answers. Descriptive statistics will be used to present patient demographic and clinical data.

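### The pre-video willingness answer, the nearest thing to a baseline of completed SLT, is not used in the SLT comparison; using it would be a cheap gain in precision, but only once it is asked at the same point in both arms

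*Combined protocol and SAP*

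**What the plan says.** Section C.3 sets the size: "Those enrolled will be randomized to either the SLT Educational Intervention group (n=20) or the Usual Care group (n=20". Section D.1.a defines the outcome: "The primary outcome measure is the number of patients who complete an SLT over the study period", and adds that "Rates of SLT procedures will be compared between patients enrolled in the SLT Educational Intervention group versus the Usual Care group". It names no test, covariate or stratification for this.

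Section F names one test, and gives it to the survey: "Fisher's exact test for count data will be used to compare the pre- and post-SLT Educational Intervention survey answers". Its only other analysis statement is "Descriptive statistics will be used to present patient demographic and clinical data".

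The heading of D.2.a places its items: "Questions for Patients in Both Groups after Consenting and Eye Exam". They include "Would you consider having laser treatment? Why or why not". Under C.4 an Intervention patient answers D.2.a first, and only afterwards: "The patient will then review the SLT Educational Intervention and be shown the PowerPoint presentation about SLT". That patient's own question time with the coordinator follows the presentation. In Usual Care the order differs: the coordinator first answers the patient's questions about treatment options, then asks D.2.a. C.4 describes patients in both arms as already randomised when they see the ophthalmologist.

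D.1.a also says how a positive result would be read: a significant rise in SLT would point to patient understanding as the main barrier.

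**The concern.** A patient's stated willingness to have laser, taken before the video, is plausibly a strong predictor of whether that patient goes on to have SLT. With 20 per arm, a few more willing patients on one side can visibly move the observed difference. The item is already collected in both arms, so leaving it out of the comparison gives up precision that would cost almost nothing.

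Interpretation is also at stake. Intervention patients get the education and also help with booking; Usual Care patients get a phone number. A higher SLT rate could come from changing reluctant patients' minds or from booking patients who were already willing. SLT counts by arm within willingness groups are the planned data closest to that question, and the reading in D.1.a depends on it. At 40 patients such counts can only be descriptive.

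**Working it through.** The plan gives no power, alpha, expected SLT rate, willing share or correlation, so there is no stated figure to reproduce. From the documents: 20 per arm and a binary outcome. Assumed: a two-sided 5% test and all rates below.

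**1. Chance imbalance.** With willing counts A and B independent Binomial(20, w), the sum of P(A=a)P(B=b) over |a−b| ≥ 4 (20 points or more) is 22.6% at w = 0.3 and 26.8% at w = 0.5. A 20-point gap shifts the unadjusted SLT difference by 0.2 × (SLT rate if willing − SLT rate if unwilling):
- weak predictor (15% / 5%): 0.2 × 0.10 = 2 points
- moderate (30% / 2%): 0.2 × 0.28 = 5.6 points
- strong (50% / 2%): 0.2 × 0.48 = 9.6 points

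**2. Power if the answer is measured alike in both arms.** Simulation, 50% willing, 6,000 runs per row. The stratified exact test conditions on the margins in each willingness stratum and sums the hypergeometric distributions. CMH is the Cochran-Mantel-Haenszel test. SLT rates are willing / unwilling.

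| Predictor | Usual Care | Intervention | Fisher → stratified exact | Chi-square → CMH |
|---|---|---|---|---|
| Strong | 50% / 2% | 85% / 25% | 35.1% → 53.8% (+18.7) | 46.6% → 63.6% (+17.0) |
| Moderate | 30% / 2% | 65% / 15% | 28.5% → 37.0% (+8.5) | 40.9% → 46.1% (+5.2) |
| Weak | 15% / 5% | 50% / 30% | 48.7% → 53.0% (+4.3) | 61.3% → 60.7% (−0.6) |
| None | 10% / 10% | 40% / 40% | 49.0% → 51.9% (+2.9) | 62.3% → 60.8% (−1.5) |

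Two further scenarios, Fisher → stratified exact: 59.4% → 72.7% (50% willing; 25% / 0% against 75% / 20%) and 28.1% → 37.3% (30% willing; 20% / 2% against 70% / 10%). In the last two table rows the 3 to 4 points over Fisher vanish in the chi-square and CMH pair. They reflect the discreteness of Fisher's test, not information from the answer.

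**3. What happens if the answer is used as now scheduled.** Suppose there is no true arm effect, and the Usual Care question session turns 30% of unwilling answers into willing without changing SLT uptake. Take 50% willing and SLT 40% / 2%, with expected counts:
- Usual Care, recorded willing: 10 + 0.3 × 10 = 13 patients, SLT rate (10 × 0.40 + 3 × 0.02) / 13 = 31.2%. Recorded unwilling: 7 patients, 2%.
- Intervention: 10 willing at 40%, 10 unwilling at 2%.
- Stratum differences: 40 − 31.2 = 8.8 points, and 0.
- Weights n1·n0/N: 10 × 13/23 = 5.65, and 10 × 7/17 = 4.12.
- Weighted difference: 8.8 × 5.65 / (5.65 + 4.12) = 5.1 points towards the Intervention, where the truth is 0.

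Simulation of the same 30% shift, stratified risk difference and stratified exact test:

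| Willing | SLT willing / unwilling | Bias | Type I error |
|---|---|---|---|
| 50% | 40% / 2% | +5.3 points | 4.5% |
| 50% | 60% / 2% | +7.8 points | 6.2% |
| 50% | 80% / 2% | +10.8 points | 8.9% |
| 30% | 60% / 2% | +9.3 points | 8.6% |

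Fisher's unadjusted test stays at 2% to 3% throughout. Without any shift, the stratified exact test runs at about 2.5% to 2.8%.

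**The case against.** The strongest case against is that nothing here is an error. Randomised arms can be compared without adjustment, and chance imbalance is already allowed for in the p-value and confidence interval. The study is a pilot that makes no power claim, so no stated figure is undermined. All of that stands. A reader might infer from the imbalance figures that the planned comparison is biased or invalid; the documents do not support that.

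Second, D.2.a is not a true baseline. It comes after randomisation, from a coordinator who also shows the presentation, and after question time in one arm only. This also stands, and it rules out the other tempting reading, that the D.2.a answer could simply be added to the analysis as it is. Step 3 shows that doing so can be worse than the present plan, and that the harm grows with the strength of prediction, which is also where the gain is largest.

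Third, the item has no response categories, and D.1.a says that the questions will still be revised. A yes against no/unsure split is therefore a proposal, but the pending revision is also the chance to close the item.

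Fourth, Section F names no test at all for completed SLT, so Fisher's test is the natural comparator here and not the plan's stated choice. That is the larger gap. It does not remove this point: a method must be written in any case, and stratification adds one clause to it.

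**Conclusion.** The point holds as a low-cost improvement, not as a correction of an invalid analysis. The text available plans no use of the willingness answer in the SLT comparison. Measured alike in both arms, it would add about 9 to 19 points of power over Fisher's exact test if it predicts SLT moderately to strongly, and about none if it predicts weakly or not at all. Every rate behind that range is assumed, so a gain is not assured. Under the current order of procedures the answer should not be used for adjustment: a 30% shift among unwilling Usual Care patients, also an assumption, biases the stratified difference by about 5 to 11 points and takes the exact test's type I error to about 5% to 9%. The change in timing is therefore a condition of the analysis change.

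**What to change.** 1. In C.4 and D.2.a, ask one closed willingness item (yes / no / unsure) at the same point in both arms. Preferably this is after consent and before randomisation; at minimum it is before any coordinator discussion of treatment in either arm.
2. In D.1.a and Section F, name the primary method: completed SLT compared between arms by an exact test stratified by that answer (yes against no/unsure), with a stratum-weighted risk difference and 95% confidence interval. Report the unadjusted comparison alongside.
3. Show SLT counts by arm within each willingness stratum, labelled as descriptive.

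The cost is a small reordering of the coordinator's script, or of the moment of randomisation, plus two or three sentences of analysis text and a few lines of R. It needs no extra patients. The downside is little or no gain if the answer predicts uptake weakly. If the timing cannot be changed, keep the unadjusted comparison as primary and do not adjust for D.2.a.

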PGAs provide greater health-related quality of life relative to LTP. The results supported that LTP can confer greater value since PGAs are 25% less effective due to poor patient adherence (21). A cost analysis by Cantor has shown that SLT is less expensive when compared with the cost of a topical generic glaucoma medication over a 5-year period. Patients treated with SLT initially, then followed by topical medication, had a cost saving of \$2.50 for every \$1.00 spent (25). Another observational study conducted by Seider found that SLT would be less costly than generic medication after 13.1 months (24). A 6-year cost comparison of SLT to primary medical therapy in Canada found that over a 3-year scenario, patients using SLT primary over “mono, bi and tri-drug therapy produced a 6-year cumulative cost savings of \$580.52, \$2042.82 and 2266.65 per patient” (26).

**A.5. Significance:** Cost-comparative studies in Canada, Australia, and the USA have tended to favor SLT as a first-line option. For these reasons, SLT would be an excellent alternative in the treatment of glaucoma, as it is reimbursed by Medicare and other insurance companies, has fewer side effects, and unlike the use of eye drops, requires no additional effort or adherence measures on the patient's part. Although glaucoma specialists consider the effect of SLT in lowering IOP to be similar to glaucoma medications, SLT is significantly underutilized as first-line treatment in glaucoma patients (24-26). Patient-related barriers may include lack of knowledge about SLT, confusion with other types of lasers, or fear of severe post-procedure complications. Ophthalmologists' attitudes may also be based on outdated information and inaccurate beliefs about SLT. Third party payers may not understand that SLT as first-line therapy may prove more convenient for patients, and may ultimately be more cost-effective (24-26).

**B. Study Aims:** The aims of this study are to:

**AIM 1:** Develop an Educational Intervention to directly inform patients with glaucoma of the benefit/risk of SLT versus ocular medications while also indirectly educating staff and physicians.

**AIM 2:** Conduct a randomized controlled trial to measure the effectiveness of an Educational Intervention with a group of patients by comparing conversions to SLT in the follow-up visits between the Usual Care group and the Educational Intervention group.

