**C.5. Tracking Outcomes:** The goal of Aim 1 is to determine if the SLT Educational Intervention used by the research coordinator and physicians with patients could lead to greater utilization of SLT by patients. Rates of SLT will be tracked in each group after patients are asked the first set of questions and after the Intervention group is shown the video. Follow-up eye exam appointments for patients in both groups will be tracked for a 6-month period to

assess the number of patients who elect to have SLT. The rate of SLT will be compared between the SLT Educational Intervention group and the Usual Care group at these time periods.

Patients will provide their name and date of birth on the consent form, both of which will be used to extract and de-identify data from their electronic medical record, including demographics, disease severity, and prior and current glaucoma treatments. Demographic data will include race/ethnicity, gender, and age.

**C.6. Assess Ophthalmologists' Beliefs and Attitudes about Laser (AIM 3):** A total of 15 glaucoma specialists and 20 general ophthalmologists will be interviewed by the research coordinator via telephone or in person. These ophthalmologists will be recruited from the Wills Eye Hospital Glaucoma Service, Wills Eye Hospital Primary Eye Care Service, Wills Eye Medical Staff, community ophthalmologists affiliated with Wills Eye Hospital, and other ophthalmologists as needed. We will recruit these ophthalmologists by asking for their input in helping patients make informed decisions about glaucoma treatment and management and assess how they approach patients with glaucoma.

These ophthalmologists, who will be asked to fill out a survey, will be considered study subjects and will be requested to sign an informed consent form prior to participation. After obtaining informed consent, we will request their input to answer several questions over the phone. Once they agree to participate and complete the phone screening questions, the research coordinator will send them a link to the Powerpoint slides including the video, and request they complete a survey (survey monkey) after viewing the intervention (See Section D.2.c).

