**D.2.b. Questions for Intervention Patients After Viewing the Presentation and Video**

Did you have any questions about the educational program we showed you?  
Would you consider having laser therapy to treat your glaucoma?  
Would you consider having this laser therapy instead of filling your prescription for eye drops?  
If no or maybe, let's discuss why?  
If yes, can I help you to schedule a laser appointment at your convenience?

In order to assess the beliefs and attitudes of a group of ophthalmologists about SLT as first line therapy before and after viewing Educational Intervention, we will ask the following questions to determine how they approach newly diagnosed patients with glaucoma.

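### Completed SLT is the primary outcome, but the only stated way to count it over 6 months is through follow-up eye exam appointments, so some procedures may be missed

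*Combined protocol and SAP*

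**What the plan says.** **Outcome.** D.1.a: "The primary outcome measure is the number of patients who complete an SLT over the study period".

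**How it is counted.** C.5 and D.1.a give the same route: "Follow-up eye exam appointments for patients in both groups will be tracked for a 6-month period to assess the number of patients", and the sentence ends with patients who elect SLT, not patients who complete it. Aim 2 (section B) also ties the comparison to visits: "comparing conversions to SLT in the follow-up visits between the Usual Care group and the Educational Intervention group".

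**A second data source.** C.5 uses patients' identifiers to "extract and de-identify data from their electronic medical record, including demographics, disease severity, and prior and current glaucoma treatments". This covers both groups alike. It is not named as the source of the primary outcome, and no extraction date or window is given.

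**Booking, Intervention.** C.4: "If the patient elects to schedule an SLT after the Educational Intervention, they will be assisted with making this appointment". The interview after the video (D.2.b) includes the offer: "If yes, can I help you to schedule a laser appointment at your convenience".

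**Booking, Usual Care.** C.4: a patient who chooses SLT during the study is told that "we will provide the phone number for them to schedule the procedure", and "Patients in the Usual Care group will not be assisted with making any SLT appointments".

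**Contacts common to both arms.** The coordinator meets both groups after the eye exam, both answer the D.2.a questions, and requests to speak to the ophthalmologist again are tracked in both, with their outcome.

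**Not stated.** The published text gives no visit schedule, no contact at the end of follow-up, no question about SLT done elsewhere, and no rule for patients who do not return.

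**The concern.** The endpoint is a procedure, but the counting rule follows appointments. Section C.3 restricts entry to patients with stable pressure, and no follow-up interval is set, so the plan does not assure a visit within 6 months. A patient who has SLT at another practice, or who does not come back, could be counted as having had none. The plan does not say whether a non-returner is scored as no SLT, left out, or treated as unknown.

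The arms also differ in what the study team learns. Helping an Intervention patient to book gives the team a date on which completion can be checked. A Usual Care patient books alone, so the team may have no such date. If leads of this kind are how completions come to be confirmed, under-counting could be heavier in Usual Care, which would favour the Intervention.

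The move from completing to electing SLT within D.1.a adds to this. If election is what gets counted, an assisted booking could itself be scored.

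This point is about detecting the outcome. Whether booking help raises uptake is a separate question about what the trial's effect measures.

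**Working it through.** The plan gives no expected SLT rate, power, significance level, return rate or rate of treatment elsewhere, so there is no figure of its own to reproduce. Section F names Fisher's exact test for survey answers only and no test for SLT rates. What follows is illustration, with assumptions marked.

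**Inputs from the documents:** 20 patients per arm (C.3); a binary outcome, SLT completed or not (D.1.a); enrolment to January 30, 2018 and analysis complete by June 30, 2018 (E).

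**Assumptions:** the same true SLT rate p in both arms; a share m of Usual Care SLTs missed and none missed in the Intervention arm (the unfavourable case); Fisher's exact test at two-sided 0.05; each arm's count Binomial(20, observed rate), all outcomes enumerated.

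**1. Weight of one patient.** 1/20 = 5 percentage points.

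**2. Loss in Usual Care only.** False difference = p − p(1 − m) = p × m. Expected missed SLTs = 20 × p × m. At p = 30% and m = 20%, that is 0.30 × 0.20 = 6 points, or 1.2 patients.

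| True rate p, both arms | False difference at m = 10 / 20 / 30% (points) | Chance of false significance favouring Intervention, m = 0% | Same chance, m = 10 / 20 / 30% |
|---|---|---|---|
| 10% | 1 / 2 / 3 | 0.6% | 0.7 / 0.9 / 1.1% |
| 30% | 3 / 6 / 9 | 1.2% | 2.1 / 3.3 / 5.2% |
| 50% | 5 / 10 / 15 | 1.0% | 2.3 / 4.7 / 9.1% |

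**3. Equal loss in both arms.** Observed rates are p(1 − m) in each arm, so the difference is 0. At p = 30% and m = 20%, both arms show 24%, and the chance of false significance favouring the Intervention is 1.2%, the same as with no loss. If true rates differ, equal loss shrinks the gap by the factor (1 − m): an assumed 50% against 30% becomes 40% against 24%, or 16 points in place of 20. That works against the Intervention.

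**4. Sensitivity to one missed Usual Care SLT.** An observed 5 against 0 gives p = 0.047; a true 5 against 1 gives p = 0.18. An observed 10 against 3 gives p = 0.041; a true 10 against 4 gives p = 0.096.

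**5. Timeline.** June 30, 2018 less 180 days is January 1, 2018. Patients enrolled after about that date cannot reach day 180 before the analysis is due to be finished. For a patient enrolled on January 30, day 180 is July 29, 2018. The plan's own 6-month follow-up already has this conflict.

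**The case against.** The strongest reply is the record extraction in C.5. It sits in the outcome-tracking section, covers all patients and includes treatments. An SLT done at the hospital is itself a contact with the site and would be expected in that record in either arm, whether or not a later eye exam takes place. This stands, and it confines the likely gap mainly to SLT done elsewhere. It does not close the gap: the record is not named as the outcome source, nothing says it is read at 6 months, and it would not reliably show treatment by another provider.

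A reader might infer that SLTs are in fact missed, and missed more often in Usual Care. The documents do not support that:

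- Appointments are to be tracked in both groups under the same wording. The text does not say that only attended visits count.
- A Usual Care patient who gets the number from the study team has told the team of the choice. The number may also lead to the same service, though the text does not say so.
- A known booking is not a completed SLT. It is at most a lead.
- If having laser tends to bring patients back, many non-returners are true non-events, and scoring them as no SLT would be largely correct.

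The missed shares used above are assumed, and none missed in one arm with 30% in the other is an extreme case. With equal loss and equal true rates there is no false difference, and at a 10% true rate the false difference is 1 to 3 points.

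**Conclusion.** The concern holds in a limited form. The plan does not name an outcome source that matches its endpoint, does not fix the date on which it is read, and does not say how non-returners or SLT done elsewhere are handled. Completed SLTs may be missed for these reasons.

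Uneven under-counting between the arms is possible because the booking routes differ, and it would favour the Intervention. Its size is unknown and it may be nil. Under the assumptions above, the false difference ranges from 1 to 15 points across true rates of 10% to 50% and missed shares of 10% to 30% in Usual Care alone. These figures show how sensitive 20 per arm is; they do not estimate the bias. The firm figure is 5 points per missed patient, enough to decide a borderline result.

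This should be settled before the outcome is collected. It does not show that the comparison is biased as designed, and if the sponsor already intends the medical record to be the source, much of the remedy is to say so and date it.

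**What to change.** In C.5 and D.1.a, replace appointment-based tracking with one source applied identically to all 40 randomised patients, whether or not they return:

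- At day 180 from randomisation, search the procedure and billing record for completed SLT, preferably by someone masked to group.
- After that date, make one scripted telephone call to every patient asking about SLT anywhere, with its date. Calling after the outcome date keeps the call from prompting an SLT inside the window.
- Count completed SLT only, not election or booking, and make the wording of D.1.a consistent with this.
- Use all randomised patients as the denominator. Report how many were not reached in each arm, with a best-case and worst-case analysis. Each patient of unknown status widens that arm's possible rate by 5 points.

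**Cost.** Up to 40 short calls and one record query, which the existing coordinator can arrange, plus a line in the protocol and consent form. Section E must also be reconciled, by moving either the last enrolment date or the analysis date, because patients enrolled after about January 1, 2018 cannot reach day 180 by June 30, 2018. That change is needed for the plan's own 6-month follow-up in any case.
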